Upon signing the informed consent document, subjects will be randomized to either the immediate monitoring group or delayed monitoring group by random number generator. The random number generator uses Ruby's pseudo-random number generator functionality (PRNG) implemented as a modified Mersenne Twister with a period of 2**19937-1. The subject's group assignment will be sent to the STSI coordinating team. Continued eligibility of all randomized subjects for the study will be confirmed upon enrollment using Aetna databases for all inclusion and exclusion criteria.

For subjects randomized to the immediate monitoring group, the first Zio patch will be sent upon confirmation of continued eligibility. The first Zio patch will be worn by subjects in the immediate monitoring group during the first two weeks of the 4-month monitoring period. A second Zio patch will be sent to subjects in the immediate monitoring group for wear during the final two weeks of the 4-month monitoring period.

A subject will be considered withdrawn from the study if they inform the STSI study coordinating center that they wish to withdraw or if they have not initiated use of the first Zio patch after 3 notifications (e-mail/phone/e-mail) from the coordinating center.

Intention-to-treat analysis for the RCT will include all participants who are enrolled in the study according to their randomly assigned group (immediate monitoring or delayed monitoring) with the RCT follow-up time for subjects in the immediate monitoring group beginning at date of enrollment and ending at 4 months following date of enrollment or the time of completion of monitoring with their final patch, whichever is longest, and for subjects in the delayed monitoring group beginning at date of enrollment and ending at 4 months following the date of enrollment.

The per protocol analysis of the RCT will include immediate monitoring participants had analyzable data from the Zio patch for at least 30 continuous minutes any time during their assigned monitoring period and all participants in the delayed monitoring group who did not withdraw from the study prior to 4 months of follow-up.

Delayed Monitoring Group

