7. STATISTICAL METHODOLOGY

Sample Size Determinations

For the 4-month RCT, the sample size of 1,000 subjects for each group (immediate monitoring = active monitoring and delayed monitoring=no active monitoring) achieves >99% power to find a difference between an expected incident atrial fibrillation rate of 5% in the active monitoring group and an expected incident atrial fibrillation rate of 0.5% group without active monitoring with a two-sided alpha of 0.05. This sample size also achieves adequate power for the detection of the difference between the two groups at lower event rates, achieving 98% power for an expected rate of 2% in the active monitoring group and 0.1% in the delayed monitoring group with a two-sided alpha of 0.05.

For the Matched Observational Cohort Study, at 12 months, sample sizes of 2,000 subjects in the active monitoring group (immediate monitoring + delayed monitoring) and 4,000 subjects in the matched control group achieves >99% power to find a difference in the expected atrial fibrillation rate of 7% in the active monitoring group and 2% in the matched control group with a two-sided alpha of 0.05.

For the Matched Observational Cohort Study, based on an expected prevalence of atrial fibrillation of 10% in both the actively monitored (i.e., n=200) and matched control cohorts (i.e, n=400), a 7.5% event rate/year in the matched observational cohort and a 50% reduction in events in the actively monitored cohort due to earlier diagnosis prior to having an event or symptom, the expected combined event rate is 5% in the actively monitored subjects and 12% in the matched observational controls. Given these assumptions, the sample size yields 81% power to detect the expected difference in time to event with a log rank test with a two-sided alpha of 0.05.

Descriptive Statistics

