The primary analysis will compare the proportion of subjects newly diagnosed with atrial fibrillation (numerator) per number of total number of subjects in the randomized group (denominator) during the first 4 months of the study between the immediate monitoring (intervention group) and delayed monitoring (control) groups using Fisher's exact test. Multivariable analysis of the primary outcome will also be performed using binomial multivariable logistic regression models to include baseline demographic (age, sex, race/ethnicity, median household income, geography, insurance type), and co-morbidity covariates. The primary analysis will be conducted with the endpoint (AF/atrial flutter) defined by any event in the Aetna databases with the ICD-9/ICD-10 code for AF/atrial flutter. Secondary analysis will be conducted using the same methods with the AF/atrial flutter endpoint defined by the HPD.

Intention-to-treat analysis will include all subjects who were randomized to the immediate monitoring or delayed monitoring groups and follow-up for outcomes from the device and the Aetna databases will be from date of enrollment to time of completion of monitoring with final patch or 4 months following enrollment, whichever is longest.

A per-protocol analysis will also be performed which will be limited to subjects in the immediate monitoring group who has a Zio patch reading of a total of at least 30 minutes and all subjects randomized to the delayed monitoring group.

Analysis of Matched Observational Cohort Study—12 month Follow-up

Analyses for the Matched Observational Cohort Study will involve comparison of outcomes in the actively monitored group from the randomized controlled trial (intervention = exposure to Zio patch monitoring) and the matched controls. Analysis at 12-month follow-up will include

the outcomes of new atrial fibrillation diagnosis and new prescriptions for 1) anticoagulants and 2) other AF-related medications.

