We will use the same time to event analyses with 3 year follow-up to evaluate the same disease and hospitalization endpoints among the subset of subjects included in the matched observational cohort study who receive a diagnosis of atrial fibrillation during the study. All analyses will be performed as intention-to-treat with parallel exploratory analyses performed on per-protocol basis restricted to subjects enrolled in the monitoring group who underwent Zio patch monitoring.

Analysis of Safety Endpoints

For analysis of safety endpoints at 3 year follow-up, we will compare incidence of hospitalization for bleeding per person-years of follow-up between the actively monitored group and the matched observational control group. Hospitalizations for bleeding will also be characterized by length of stay. Other safety outcomes will be characterized for the period of active monitoring in the active monitoring group only. These include Incidence of non-AF, but other actionable heart rhythms captured by the Zio patch device, specifically: 1) Atrial Tachycardia with variable block of > 30 seconds; 2) Ventricular Tachycardia >5 beats; 3) Pauses \geq 5 seconds; and 4) AV block. We will also characterize early discontinuation of active monitoring in monitored cohort by cause and time to event.

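### The SAP gives two conflicting definitions of the RCT per-protocol set, both comparing patch wearers with essentially unselected controls; the 4-month error is small and cheap to remove

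*SAP*

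**What the plan says.** The RCT per-protocol set is defined in two places in the SAP.

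- **Section 4, Randomized Controlled Trial Population.** Immediate-arm participants qualify if they "had analyzable data from the Zio patch for at least 30 continuous minutes any time during their assigned monitoring period". From the other arm it takes all "participants in the delayed monitoring group who did not withdraw from the study prior to 4 months of follow-up".
- **Section 7, Analysis of Randomized Controlled Trial.** The set is immediate-arm subjects with a "Zio patch reading of a total of at least 30 minutes and all subjects randomized to the delayed monitoring group".

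The matched cohort study has the same looseness. Section 4 takes RCT subjects with at least 30 continuous analysable minutes during the RCT who did not ask to be removed from follow-up, together with their matched controls. Section 7, under the 3-year follow-up, describes exploratory per-protocol analyses "restricted to subjects enrolled in the monitoring group who underwent Zio patch monitoring", with no minimum duration.

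In both the RCT and the 12-month analysis, per-protocol comes after intention-to-treat. Only the 3-year per-protocol analysis is called exploratory.

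**The concern.** There are two separate problems.

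First, the RCT definitions differ in both arms: continuous against total minutes, analysable data against any reading, and withdrawn controls out against in. With no rule of precedence, the set could be chosen after the results are known.

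Second, under either definition an immediate-arm subject enters by doing something after randomisation, namely wearing the patch. Delayed-arm subjects get no patch until month 4, so those who would never have worn one cannot be identified and stay in. Only an actual withdrawal can remove a control, and only under Section 4. If wearers and non-wearers differ in background risk, the contrast mixes that difference with the effect of monitoring. What is at stake is the reported yield among people who actually wear the patch, which a screening programme would want to know. Neither document plans an estimate of it that keeps the randomised comparison.

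**Working it through.** **Inputs from SAP Section 7, Sample Size Determinations:** "the sample size of 1,000 subjects for each group"; an "expected incident atrial fibrillation rate of 5% in the active monitoring group"; "an expected incident atrial fibrillation rate of 0.5% group without active monitoring"; two-sided alpha 0.05. **Not in the documents:** patch uptake, written *c*. I take 60% to 95% as an assumed range.

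**1. The plan's own figures.** For 5% against 0.5%, power is 0.99999 by the pooled normal formula and above 0.9999 by enumeration of Fisher's exact test; the SAP says above 99%. For 2% against 0.1% the values are 0.987 and 0.997; the SAP says 98%. The sample size is not in question.

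**2. Intention-to-treat difference.** 5.0 − 0.5 = 4.5 points. SE = √(0.05×0.95/1000 + 0.005×0.995/1000) = 0.72 points; 95% CI 3.1 to 5.9; z = 4.5/0.72 = 6.2.

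**3. Complier-average effect.** Controls cannot get the study patch before month 4, so non-adherence is one-sided. If assignment acts only through wearing the patch, the effect among wearers is 4.5/*c*, with SE about 0.72/*c*.

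**4. Error of the per-protocol contrast (Section 7 set).** The per-protocol difference is the wearers' rate minus the rate in all controls. The complier-average effect is the wearers' rate minus the rate in controls who would have worn the patch. The error is therefore p0(would-be wearers) − 0.5%. Since p0(would-be wearers) lies between 0 and 0.5%/*c*, the error lies between −0.5 and +0.5×(1/*c* − 1) points. If never-wearers have twice the wearers' background rate (assumption), p0(would-be wearers) = 0.5/(*c* + 2(1 − *c*)).

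| Assumed uptake *c* | Effect 4.5/*c* (points) | SE | Error, never-wearers at twice the rate | Upper limit of error |
|---|---|---|---|---|
| 60% | 7.5 | 1.2 | −0.14 | +0.33 |
| 65% | 6.9 | 1.1 | −0.13 | +0.27 |
| 80% | 5.6 | 0.9 | −0.08 | +0.13 |
| 95% | 4.7 | 0.8 | −0.02 | +0.03 |

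**5. Does the choice of set matter at 4 months?** Very little. At *c* = 80%, with 3% of controls withdrawn and all of them would-be never-wearers (assumption), the Section 4 set moves the error from −0.08 to −0.07, or from +0.13 to +0.11. As a cross-check, spread first-year drop-out evenly over the year (assumption). The SAP's 5% gives 5% × 4/12, about 17 per 1,000; the protocol's 12% gives 40. Removing 40 event-free controls moves the control rate from 5/1000 = 0.50% to 5/960 = 0.52%.

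**6. False positives.** Suppose the patch had no effect, with 0.5% in both arms. The Section 7 per-protocol Fisher test rejects about 10% of the time in an extreme case (60% uptake and no background AF in never-wearers). In the milder cases tried it rejects about 5% or less.

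**The case against.** The strongest reply is that this is a supportive analysis. The primary test keeps all randomised subjects, the per-protocol result ranks second throughout, and its 4-month error is a fraction of a point. The complier-average estimate is the intention-to-treat result rescaled by 1/*c*: estimate and SE grow together, z stays at about 6.2, and no power is gained. It also needs a common 4-month window, which the SAP does not provide. Section 4 lets only the immediate arm run past 4 months. Section 7 does not split the window by arm and, read literally, could count patch findings in the delayed arm. All of this stands, and it limits the point. It does not remove the conflict between the definitions, nor does it make either version a randomised comparison.

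Two stronger readings are tempting, and the documents support neither.

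- A reader might infer that drop-out makes the two control sets very different. The drop-out figures are first-year figures, the two documents disagree on them, and the exclusion covers only withdrawal before month 4, when failure to start a patch cannot yet occur in that arm.
- A reader might infer that selecting adherent people could by itself imitate a 3-year benefit. The documents give neither the share of non-wearers nor their relative risk. Section 4 keeps the wearers' own matched controls, the Cox models adjust for demographics and co-morbidity scores, and the SAP already calls this analysis exploratory. Residual differences linked to adherence remain possible, but their size cannot be derived from the plan.

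**Conclusion.** The point holds as a modest one. The conflict between Sections 4 and 7 is plain from the text. Both versions set patch wearers against essentially unselected controls, so neither contrast is protected by randomisation. At the plan's rates the error is at most about 0.5 points against an effect among wearers of about 5 to 7.5 points. The intention-to-treat primary result is not threatened, and the per-protocol conclusion would not change under the design assumptions.

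The size rests on the 0.5% control rate, which caps the error; a higher background rate would raise the cap in proportion. The effect range rests on assumed uptake. The case for change is that it closes an open choice and yields a better estimate at almost no cost.

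**What to change.** 1. State one per-protocol definition, covering the wear rule and the treatment of withdrawn controls. Use it for the RCT and, with matched controls, for the cohort study, in Sections 4 and 7, before analysis. Clarify the cohort wording that ties wear to the RCT period: delayed-arm patches start after that period, so a literal reading could exclude that arm.
2. For the RCT, report the complier-average effect in place of, or ahead of, the per-protocol test: the intention-to-treat risk difference divided by the share of the immediate arm with any recorded Zio wear, with a bootstrap CI. Use any wear rather than a 30-minute threshold, because 30 seconds of AF can be found in less than 30 minutes. Count outcomes in both arms over the same fixed 4 months from enrollment, so that no delayed-arm patch findings enter.
3. Label the 12-month wearer-only analysis exploratory.

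The cost is SAP wording and one ratio from data already collected. The interval is wider than for intention-to-treat, no power is added, and the estimate assumes that assignment affects AF diagnosis only through wearing the patch. The protocol starts the monitoring clock at device activation, so a second patch can run beyond 4 months from enrollment; later findings would be left out of this estimate.

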3. ANALYSIS OBJECTIVES

The analysis objectives corresponding to the study objectives listed in 1. INTRODUCTION AND BACKGROUND are the following:

Primary Analysis

1. Compare incidence of newly diagnosed atrial fibrillation (as defined by ≥ 30 seconds of atrial fibrillation or flutter detected by device, or a new clinical diagnosis recorded in claims data) at the end of the 4-month monitoring period in the immediate monitoring cohort (n=1,000) with delayed monitoring cohort (control group) (n=1,000) using ICD-9/ICD-10 codes.

Secondary Analyses

1. Compare time to first event of newly diagnosed atrial fibrillation (as defined by ≥ 30 seconds of atrial fibrillation or flutter detected by device, or a new clinical diagnosis recorded in claims data) at the end of the 4-month monitoring period in the immediate monitoring cohort (n=1,000) with delayed monitoring cohort (control group) (n=1,000) using ICD-9/ICD-10 codes.
2. Compare incidence of newly diagnosed atrial fibrillation (as defined by ≥ 30 seconds of atrial fibrillation or flutter detected by device, or a new clinical diagnosis recorded in claims data) at the end of the 4-month monitoring period in the immediate monitoring cohort (intervention group) (n=1,000) with delayed monitoring cohort (control group) (n=1,000) using HPD definition.
3. Compare prevalence of atrial fibrillation in the actively monitored cohort (n=2,000) with the matched observational control cohort (n=4,000) at 12 months.
4. Compare time to event of newly diagnosed atrial fibrillation in the actively monitored cohort (n=2,000) with the matched observational control cohort (n=4,000) at 12 months.
5. Compare the rate of initiation of anticoagulation therapy in the actively monitored cohort with the matched observational control cohort at 12 months.
6. Compare the rate of initiation of other atrial fibrillation-related therapies (antiarrhythmic agents excluding beta-blockers and calcium channel blockers, cardioversions, ablation procedures or hospitalizations with a primary diagnosis of AF) in the actively monitored cohort with the matched observational control cohort at 12 months.
7. Compare utilization in actively monitored cohort with the matched observational cohort at 12 months.
8. Compare time to first event of the combined endpoint of stroke, systemic embolism, or myocardial infarction in the actively monitored cohort with the matched observational control cohort at 3 years:

- a. In the entire cohorts.

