6. HANDLING OF MISSING DATA

Missing data will be quantified for all variables. Given that endpoints are based on claims data, endpoints that do not appear in the claims data are measured as zero or absent and are thus not considered missing during the time that the subject remains enrolled in Aetna. Medical and pharmacy coverage will be assessed to identify truly missing data from zero/absent. For time to event analyses, subjects are censored at time of disenrollment. In addition, age and sex were included in the inclusion criteria for all subjects, and thus are not anticipated to be missing. Patterns of missing-ness of other covariates will be assessed by determining bivariate associations of the missing data (have data/do not have data) with demographic variables and co-morbidity scores. Variables found to be significantly associated with missing data will be used as covariates in the multivariable models used for the primary and secondary endpoints.

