The analysis will compare the proportion of subjects with newly diagnosed atrial fibrillation (numerator) per number of total number of subjects in group (denominator) during the first 12 months from the date of enrollment of the actively monitored subject between the actively monitored cohort and matched observational cohort using Fisher's exact test. Multivariable analysis of the AF/atrial flutter outcome will also be performed using binomial multivariable logistic regression models to include baseline demographic (age, sex, race/ethnicity, median household income, geography, insurance type), co-morbidity covariates. The same analysis will be performed for the other 12-month follow-up outcomes of new prescription for anticoagulation medication and new prescription of other AF-related medications. All analyses will be conducted first as intention-to-treat and second among the per-protocol population.

Matched Observational Cohort Study – 3 year Follow-up

Analyses at 3 years of follow up will focus on time to event for disease outcomes (stroke, myocardial infarction, and systemic thromboembolism) and hospitalizations (all-cause and for bleeding) compared between the actively monitored cohort and the matched observational control cohort after 3 years of follow-up. Bivariate time-to-event analysis will be conducted using Kaplan-Meier analysis with the time to event calculated from the date of the enrollment of the actively monitored subject and the date of the first event of the specific disease outcome (separate analysis for each outcome). Subjects not having an endpoint event during the observation period will be censored at the end of the 3-year follow-up or date of discontinued enrollment from Aetna. Multivariable analyses will be conducted using Cox proportional hazard models and will include potential confounders including age, sex, race/ethnicity, insurance type, variables related to geography and co-morbidity scores. For the Cox models, if assumptions of proportionality are not met (as assessed by Kaplan-Meier and plots of Schoenfeld residuals), models accounting for non-proportionality (using time*covariate interaction terms) will be run.

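### The 12-month proportions count members who leave Aetna, or whose pharmacy fills cannot be seen, as event-free; SAP Section 6 does not support this, and the direction of the bias is uncertain

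*SAP*

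**What the plan says.** SAP Section 7 (Matched Observational Cohort Study, 12-month follow-up) defines the AF result as subjects newly diagnosed "per number of total number of subjects in group (denominator) during the first 12 months", compared "between the actively monitored cohort and matched observational cohort using Fisher's exact test" and then by logistic regression. It continues: "The same analysis will be performed for the other 12-month follow-up outcomes of new prescription for anticoagulation medication", and likewise for other AF-related medications. It sets no requirement for 12 months of membership or for pharmacy coverage.

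SAP Section 6 limits the reading of an absent claim as no event. Such endpoints "are thus not considered missing during the time that the subject remains enrolled in Aetna". It adds: "Medical and pharmacy coverage will be assessed to identify truly missing data from zero/absent". Its only rule for people who leave is "For time to event analyses, subjects are censored at time of disenrollment". The rest of its missing-data modelling concerns covariates.

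SAP Section 3, secondary analysis 4, lists a censorable 12-month analysis for AF ("Compare time to event of newly diagnosed atrial fibrillation in the actively monitored cohort (n=2,000"). Section 7 gives no model for it, because Kaplan-Meier and Cox are described only for the 3-year follow-up. Secondary analyses 5 and 6 (anticoagulation and other therapies) have no time-to-event counterpart at 12 months.

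**The concern.** The two sections do not fit together. Under Section 6, time after leaving Aetna is unobserved. Under Section 7, the same time counts as event-free. A coverage check is promised, but nothing says what happens to a subject whose endpoint proves to be truly missing in a proportion. At 3 years the SAP handles the problem by censoring at the end of Aetna enrolment.

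The groups may not be affected alike. Control AF can come only from claims, whereas AF in the monitored cohort can also come from the patch (Protocol section 4), and patch findings sit in a study database. Participants volunteered and controls were never invited. SAP Section 4 matches on sex, year of birth and CHA2DS2-VASc score, not on pharmacy coverage. Equal membership loss and equal drug coverage are therefore assumptions. At stake are the size of the 12-month AF effect and the validity of the anticoagulation and other-therapy comparisons.

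**Working it through.** **Inputs**
- 7% versus 2% AF at 12 months; 2,000 versus 4,000 subjects; two-sided alpha 0.05; power above 99% (SAP Section 7, sample size).
- 5% AF at 4 months under monitoring (Protocol section 7). I use it to treat 5 of the 7 monitored points as device detections that survive leaving Aetna. This is an assumption, since the endpoint at 4 months also includes clinical diagnoses.
- Disenrolment and pharmacy coverage: neither document gives a rate. The nearest figures are first-year drop-out of enrolled participants, 5% (SAP Section 4) and 12% (Protocol section 4). I assume losses of 5-20%, with 30% as an extreme.
- Loss is taken as uniform over the year with a constant event rate, so a loss of d removes d/2 of claims-based events.

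**Step 1: the plan's figure.** The normal-approximation power for 7% versus 2% with 2,000 and 4,000 subjects is above 0.9999. The stated figure of above 99% reproduces.

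**Step 2: AF under the all-subject denominator.** Observed rate = p × [r + (1 − r)(1 − d/2)], where r is the share of events retained through the patch. Monitored (r = 5/7): 5 + 2(1 − d/2). Control (r = 0): 2(1 − d/2).

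| Loss, monitored / control | Monitored % | Control % | Difference | Ratio |
|---|---|---|---|---|
| 0 / 0 | 7.00 | 2.00 | 5.00 | 3.50 |
| 5% / 5% | 6.95 | 1.95 | 5.00 | 3.56 |
| 12% / 12% | 6.88 | 1.88 | 5.00 | 3.66 |
| 20% / 20% | 6.80 | 1.80 | 5.00 | 3.78 |
| 5% / 20% | 6.95 | 1.80 | 5.15 | 3.86 |
| 20% / 5% | 6.80 | 1.95 | 4.85 | 3.49 |

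The difference is unchanged under equal loss because the assumed claims-based part in the monitored group (7 − 5 = 2 points) equals the control rate. If no patch findings are retained (r = 0 in both groups), equal loss of 5%, 12% or 20% gives differences of 4.88, 4.70 or 4.50 points and a ratio of 3.50. Power stays above 0.99 throughout.

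**Step 3: the delayed arm.** This half gets its first patch 4 months after enrolment, so its device period is about months 4-8. Suppose that leaving Aetna earlier also ends device follow-up (an assumption; the documents do not say). Then half of the 5 points, 2.5, is exposed. At 12% equal loss, 12% × 4/12 = 4% to 12% × 8/12 = 8% have left, which costs 2.5 × 0.04 = 0.10 to 2.5 × 0.08 = 0.20 points. The monitored rate becomes 6.78 to 6.68%, the difference 4.90 to 4.80 points and the ratio 3.61 to 3.55.

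**Step 4: prescriptions, claims only in both groups.** Take an illustrative true 4% versus 2%. Equal disenrolment of 5%, 12% or 20% gives 3.90/1.95, 3.76/1.88 or 3.60/1.80%. The ratio stays at 2.00 and the difference shrinks to 1.95, 1.88 or 1.80 points. An equal 5-20% without observable fills for the whole year shrinks it to 1.90-1.60 points.

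**Step 5: prescriptions with no true effect, 5% in both groups.** With 5% versus 20% loss, the observed rates are 5 × 0.975 = 4.875% and 5 × 0.90 = 4.500%. Under the normal approximation, the nominal 2.5% chance of a significant result in favour of screening becomes:
- 4.9% with loss of 5% monitored / 12% control;
- 9.8% with 5% / 20%;
- 20.2% with 5% / 30%;
- 1.2% with 12% / 5%, where the chance of a significant result against screening is 4.7%.

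**The case against.** An all-subject denominator is a conventional intention-to-treat proportion, and these are secondary, non-randomised comparisons. The SAP has partial safeguards. It lists a 12-month time-to-event AF analysis to which the Section 6 censoring rule would apply, it puts insurance type in the logistic model, and it collects follow-up months of eligibility. Section 2 lists internal and external pharmacy data, so it is not established that members without an Aetna drug benefit have no visible fills. Kaplan-Meier estimation brings its own assumption of non-informative censoring.

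Much of this stands, but it does not close the gap. The listed time-to-event analysis covers AF only and has no model. Insurance type measures neither drug coverage nor time observed. Nothing says how the result of the coverage check enters the prescription outcomes.

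A reader might go further and infer that the bias always favours screening, because controls depend on claims and monitored subjects do not. The documents do not support that. On the difference scale, equal loss gives no AF bias in Step 2 and a bias against screening in Step 3. Higher loss among participants reverses the sign, and equal loss shrinks the prescription difference. Nothing in either document says which group loses more members.

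Nor is an extra 4-month analysis needed. The 4-month proportion is also taken "per number of total number of subjects in the randomized group (denominator) during the first 4 months of the study", but Section 3, secondary analysis 1, already lists a 4-month time-to-event comparison.

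**Conclusion.** The point holds as an inconsistency between SAP Sections 6 and 7 that leaves the 12-month estimates open to bias of uncertain direction. For AF the effect is modest: in the Step 2 table the ratio runs from 3.49 to 3.86 against a planned 3.50, and the difference from 4.85 to 5.15 points against 5.00. The conclusion of the planned AF test would not change. For prescriptions the matter is more serious, since unequal loss or coverage alone creates a difference in either direction. All sizes rest on assumed loss rates, uniform loss over the year and the 5-of-7 device share; the documents supply no disenrolment or coverage rate. This should be corrected before analysis.

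**What to change.** For the 12-month AF, anticoagulation and other-therapy outcomes:
- Make the main estimate the difference in cumulative incidence at 12 months with a confidence interval (Kaplan-Meier), censored at loss of Aetna medical coverage, with death handled as a competing event where it is known.
- For drug outcomes, require observable pharmacy coverage at the index date in participants and controls alike, and censor at its loss.
- State how patch findings after disenrolment are counted.
- Report disenrolment and pharmacy coverage by group.
- Keep Fisher's test on all subjects as a supportive analysis.

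The cost is SAP wording. The change extends the plan's own 3-year censoring rule and uses eligibility data already listed in Section 5 and the coverage assessment promised in Section 6. The downsides are fewer subjects in the drug analyses and reliance on non-informative censoring, which the by-group reporting helps readers to judge.
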